### **Stratification**

Randomization will be stratified by disease severity and body weight collected at Randomization Visit. This stratification ensures balanced allocation of subjects to treatment groups within the disease severity and weight strata.

The weight strata will be “body weight < 25 kg”, “25 kg ≤ body weight < 50 kg” or “body weight ≥ 50 kg” and disease severity strata (refer to [Table 5-2](#)). Stratification by disease severity and body weight will occur at Randomization Visit.

**Table 5-2 Disease severity classification**

IGA	PASI score	Psoriasis severity
3	12-< 20	Moderate
3	≥ 20	Moderate
4	12-< 20	Moderate
4	≥ 20	Severe

It will be targeted to have at least about 5 subjects in the < 25kg weight, and at least about 10 subjects in each of the other two weight groups.

The randomization scheme for subjects will be reviewed and approved by a member of the Integrated Quantitative Sciences Randomization Group.

### **5.4 Treatment blinding**

Medication will be labeled in an open-label fashion. Blinding requirements are not applicable for any of the parties involved.

### **5.5 Treating the subject**

Sponsor qualified medical personnel will be readily available to advise on trial related medical questions or problems.

#### **5.5.1 Subject numbering**

Each subject is uniquely identified by a Subject Number assigned by Novartis. The subject number is composed of a site number and a sequential subject number. Once assigned to a subject, the Subject Number will not be reused.

Upon signing the informed consent form, the subject is assigned the next sequential number available in the electronic data capture (EDC) system. The investigator or his/her staff will contact the IRT and provide the requested identifying information for the subject to register them into the IRT. The site must select the eCRF book with a matching Subject Number in the EDC system to enter data.

If the subject fails to be treated for any reason, the IRT must be notified within 2 days that the subject was not treated. The reason for not being treated will be entered on the appropriate Screening period eCRF.

### **5.5.2 Dispensing the study drug**

Each study site will be supplied by Novartis with study treatment.

At all visits where secukinumab is dispensed, the IRT system will allocate a unique medication number which will be transmitted to the pharmacist (or other qualified site personnel) responsible for dispensation of study treatments. The pharmacist (or other qualified site personnel) will then identify the study treatment package(s) to administer to the subject corresponding to the medication number(s). The study drug packaging has a 2-part label. The unique medication number is printed on each part of this label. Immediately before preparation of the study treatment, the pharmacist (or other qualified site personnel) will detach the outer part of the label from the packaging and affix it to the source document for that subject's unique subject number. These documents will be kept in a secured location as appropriate. The study treatment will be administered by study nurse/ qualified site personnel individual.

During the COVID-19 pandemic or similar major health care disruption that limits or prevents on-site study visits, delivery of study drug directly to a participant's home is generally permitted in the event the Investigator has decided that an on-site visit by the participant is no longer appropriate or possible, and that it is in the interest of the participant's health to administer the study treatment even without performing an on-site visit. The dispatch of study drug from the site to the participant's home remains under the accountability of the Investigator.

At the site level, the agreement with approval of the Principal Investigator, Independent Ethics Committee/ Institutional Review Board (IEC/IRB) and any other Board as appropriate should be in place to implement home delivery.

#### **Home administration of secukinumab**

After Week 16, subjects/custodians will be expected to perform home administrations of secukinumab at the time points specified in the protocol, when they are not visiting the site for other trial related procedures. Subjects/custodians must be previously trained by site staff regarding the administration of secukinumab PFS.

It must be noted that subjects 12- < 18 years of age can self-inject only under caregiver or health care professional supervision. Subjects < 12 years of age are not allowed to self-inject at any time.

If the subject or custodian is not confident to administer medication at home, subjects should visit the site every 4 weeks and according to the visit schedule to have the administrations performed there by the site staff. Alternatively, if possible, local arrangements can be done for a trained nurse to administer medication to the subject at home. This person must be sufficiently trained.

For home administrations the pharmacist/ qualified site personnel will dispense, via IRT, an appropriate number of investigational treatment packages and detach outer part of the label from the packaging as indicated above. The custodians/subjects will record the date(s) of

administration at home and will return the used PFS and packaging at their next visit to the site. Site staff are to transcribe this information into the appropriate Dosage Administration Record eCRF.

The used PFS should be disposed immediately after use in a sharps container OR according to the requirements of the respective countries and brought back to site. Subjects will be asked to return all unused PFS the latest at the completion of the study or at the time of discontinuation of the investigational treatment. Detailed instructions will be provided separately.

### **5.5.3 Handling of study and additional treatment**

#### **5.5.3.1 Handling of study treatment**

Study treatment must be received by a designated person at the study site, handled and stored safely and properly, and kept in a secured location to which only the investigator and designees have access. Upon receipt, all study treatment must be stored according to the instructions specified on the labels. Clinical supplies are to be dispensed only in accordance with the protocol. Technical complaints are to be reported to the respective Novartis Country Pharma Organization Quality Assurance.

Medication labels for secukinumab prefilled syringes will be in the local language and comply with the legal requirements of each country. They will include storage conditions for the investigational treatment but no information about the subject except for the medication number. They must be stored in a secured refrigerator at 2°C-8°C (36°F-46°F), and must be carefully controlled in accordance with regulations governing investigational medicinal products and local regulations. Study treatments should not be frozen and must be protected from light.

The investigator must maintain an accurate record of the shipment and dispensing of study treatment in a drug accountability log. Monitoring of drug accountability will be performed by monitors during site visits or remotely and at the completion of the trial. Subjects will be asked to return all used PFS and packaging at frequent intervals (i.e. at next scheduled study visit) and unused PFS and packaging latest at the end of the study or at the time of discontinuation of study treatment.

At the conclusion of the study, and as appropriate during the course of the study, the investigator will return all unused PFS, packaging, drug labels, and a copy of the completed drug accountability log to the Novartis monitor or to the Novartis address provided in the investigator folder at each site.

[figure not shown]
#### **5.5.3.2 Handling of additional treatment**

Not applicable.

### **5.5.4 Instructions for prescribing and taking study treatment**

All study treatments will be administered subcutaneously throughout the study. All doses of study treatments at scheduled site visits will be administered at the study site after the study assessments for the visit have been completed. Prior to administration to the subject, the study treatment will be dispensed by the qualified site personnel appointed at the study site.

For home administrations the processes described earlier at [Section 5.5.2](#) must be followed.

The first study treatment administration will occur at the Randomization Visit (Day 1), after all study scheduled assessments have been performed (and inclusion/exclusion criteria confirmed) and only after the scheduled blood samples have been drawn. Similarly, at each other visit, all study assessments should be completed prior to the administration of study treatment.

Subjects will be administered study medication weekly for the first 4 weeks of the treatment period and then every 4 weeks until Week 204.

During the Follow-up period, no study medication will be administered.

### **Administration of secukinumab**

Secukinumab Solution for Subcutaneous Injection will be provided in Prefilled syringes (75 mg/0.5 mL and 150 mg/1mL).

The study treatment solution **must** be injected into **non-affected** areas of the skin.

If possible, throughout the trial, the study treatment should be administered to body regions, changing the injection site from visit to visit, for example: right thigh, left thigh, right abdominal area, left abdominal area.

Single prefilled syringes will be packed in individual boxes. The boxes containing the syringes with study treatment solution should be kept at 2 to 8°C (36°F to 46°F) and protected from light. They should not be frozen or shaken. Prior to administration the boxes containing the syringes with study treatment solution should be allowed to come to room temperature unopened for about 15-30 minutes before administration. Used syringes should be disposed immediately after use in a sharps container or according to the requirements of the respective countries. For home administration please refer to [Section 5.5.2](#).

Note: The removable cap of the secukinumab pre-filled syringe 1 mL and 0.5mL form contains a derivative of natural rubber latex. Although no natural rubber latex is detected in the cap, the safe use of the secukinumab 1 mL or 0.5 mL pre-filled syringe in latex-sensitive individuals has not been studied.

All kits of study treatment assigned by the IRT will be recorded/databased in the IRT.

The investigator must promote compliance by instructing the subject to take the study treatment exactly as prescribed and by stating that compliance is necessary for the subject's safety and the validity of the study. The subject must also be instructed to contact the investigator if he/she is unable for any reason to take the study treatment as prescribed.

#### **5.5.5 Permitted dose adjustments and interruptions of study treatment**

Investigational or other treatment dose adjustments and/or interruptions are not permitted.

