## Treatment Period

The treatment period is defined as randomization to Week 208. In this period the endpoints are assessed and subjects are followed for long-term safety and efficacy. Subjects will be randomized using 1:1 ratio into either secukinumab low dose or secukinumab high dose. Randomization will be stratified by body weight (< 25kg, 25-< 50 kg,  $\geq$  50kg) and disease severity (either moderate (PASI score 12-<20 and IGA 3 or 4 or PASI score  $\geq$  20 and IGA 3) or severe (PASI score  $\geq$  20 and IGA of 4), collected at Randomization Visit. The study aims to recruit at least 60 subjects with moderate disease severity and approximately 20 subjects with severe disease severity. It will be targeted to have at least 5 subjects in the < 25kg weight, and at least 10 subjects in each of the other two weight groups. Subjects will receive the appropriate dose based on their body weight category. If a subject moves into a higher or lower weight group at two consecutive visits with weight measurements during the maintenance (from Week 12 onwards as assessed at 4 weekly visits or during extension treatment period (as assessed at scheduled site visits), the subject will receive dosing according to the new (higher or lower) weight group respectively. The dose will be adapted starting from the visit of the second consecutive weight change.

Adolescents (12-< 18 years) and children (6-< 12 years) can be included from the beginning of this study, since the DMC has approved already the enrollment of children (6-< 12 years) in study CAIN457A2310.

All subjects will visit the study site at Randomization (Day 1) and at Weeks 1, 2, 3, 4, 8, 12, 16 during which they will receive either high-dose or low-dose secukinumab treatment subcutaneously. Additionally, subjects will visit the site at Weeks 13, 14, 15 to provide blood samples for pharmacokinetics.

During the Treatment period subjects will receive treatment of the assigned secukinumab dose every 4 weeks. However during Weeks 16-52 site visits will be scheduled every 8 weeks and from Weeks 64-208 site visits will be scheduled every 12 or 16 weeks, to minimize the burden on the subject. Subjects will have the option to receive treatment between scheduled visits at home, following instructions provided to the subject (if  $\geq$ 12 years old), parent or caregiver.

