a Before randomizing the subject, the site must ensure that all assessments of the screening visit have been performed, all lab results are available and subject is eligible. Special attention must be given to tuberculosis testing as results take longer to be available.

 Apart from the Informed consent for this study signed by parent(s) /legal representatives, assent form will be completed as appropriate by the pediatric subjects.

 These assessments are supported by and are stored with the source documentation. However, data regarding to which inclusion/exclusion criteria are met are captured on the appropriate eCRF

 Information on Topical Corticosteroid medication, that a subject may use, is entered in the concomitant medications-topical corticosteroids eCRF

 Measured standing and barefoot, using the same stadiometer.

 Samples will be shipped to and analyzed by the central lab. At the discretion of the investigator, laboratory assessments need not to be performed again at Day 1-Randomization (R) visit if screening labs were performed within 7 days from randomization.

 If the first tuberculosis central lab test is indeterminate, the investigator may choose to perform a second test (as part of an unscheduled visit) or refer the subject for tuberculosis workup per local guidelines. If the result of any tuberculosis central lab test is "positive" or the results of two sequential tests are "indeterminate", the subject must be referred to have a tuberculosis workup per local guidelines (if no workup within 12 weeks prior to randomization is available). The subject will not be eligible for randomization if active tuberculosis is present or if latent tuberculosis is present and is untreated as per local guidelines.

 Urine pregnancy test will be performed locally. If there is a positive urine pregnancy test, study treatment must be withheld and a serum pregnancy test done at the same visit. Pregnancy tests will be performed in female subjects of child bearing potential, i.e. those who have started menstruation and/or are of age 12 or older.

 Samples shipped by the sites will be stored at the central laboratory and then shipped to reference laboratories for analysis. Each PK and IG blood sample should be collected pre-dose between Day 1 (Randomization) and Wk 52.

 CDLQI will no longer be completed once subjects reach 18 years of age

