- action taken regarding secukinumab treatment

All adverse events must be treated appropriately. Treatment may include one or more of the following:

- no action taken (eg further observation only)
- secukinumab treatment interrupted/withdrawn
- concomitant medication or non-drug therapy given
- non-drug therapy given
- subject hospitalized/subject's hospitalization prolonged (see [Section 7.2](#) for definition of SAE)
- its outcome (not recovered/not resolved; recovered/resolved; recovered/resolved with sequelae; fatal; or unknown)

Once an adverse event is detected, it must be followed until its resolution or until it is judged to be permanent, and assessment must be made at each visit (or more frequently, if necessary) of any changes in severity, the suspected relationship to the study drug, the interventions required to treat it, and the outcome.

Worsening of psoriasis in this study is evaluated via the use of PASI, IGA mod 2011 and CDLQI assessments and is not expected to be captured as an AE in the eCRF. Exceptions include cases when a) a new type of psoriasis is diagnosed eg guttate psoriasis) or b) the worsening of psoriasis is so severe that a qualitatively different status is reached.

Information about common side effects already known about the investigational drug can be found in the Investigator Brochure (IB). This information will be included in the subject informed consent and should be discussed with the subject during the study as needed. Any new information regarding the safety profile of the medicinal product that is identified between IB updates will be communicated as appropriate, for example, via an IN or an Aggregate Safety Finding. New information might require an update to the informed consent and has then to be discussed with the subject.

The investigator must also instruct each subject to report any new adverse event (beyond the protocol observation period) that the subject, or the subject's personal physician, believes might reasonably be related to study treatment. This information must be recorded in the investigator's source documents; however, if the AE meets the criteria of an SAE, it must be reported to Novartis.

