Adverse events will be summarized by presenting, for each treatment group (including any AIN457), the number and percentage of subjects having any AE, having an AE in each primary system organ class and having each individual AE (preferred term). The relative frequencies and 95% confidence intervals within each system organ class will be presented for adverse event and serious adverse event in a panel graph (for DMC only).

Summaries will also be presented for AEs by severity and for study treatment related AEs. If a particular AE 'severity' is missing, this variable will be listed as missing and treated as missing in summaries. If a subject reported more than one adverse event with the same preferred term, the adverse event with the greatest severity will be presented. If a subject reported more than one adverse event within the same primary system organ class, the subject will be counted only once with the greatest severity at the system organ class level, where applicable.

The crude incidence of treatment emergent AEs may be repeated and presented by age, disease severity strata and by body weight strata subgroups.

The exposure time-adjusted incidence rate of treatment emergent AEs, SAEs and important identified or potential risks (level 1) in entire treatment period will be summarized, where data permits. Data will be reported by SOC and PT and presented by age, disease severity strata and body weight strata. Crude rate will also be evaluated. Summary by body weight and dose group may be evaluated in addition to the above.

Adverse events will also be reported separately by standardized or customized MedDRA queries (SMQ or CMQ/NMQ). The MedDRA version used for reporting the study will be described in a footnote.

The most common adverse events reported ($\geq z\%$ in any group for each preferred term in the SOC-PT table or $\geq z\%$ in any group for each grouping term table) will be presented in descending frequency according to its incidence in total AIN457 group (combining both AIN457 treatment groups) starting from the most common event. Here threshold value z is set to 2 (%) but it may be updated following review of the dry run outputs.

Separate summaries will be provided for study treatment related adverse events, death, serious adverse event, other significant adverse events leading to discontinuation and adverse events leading to dose adjustment or interruption.

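### Protocol 5.5.5 bans every dose adjustment and interruption, yet Section 3.1 requires weight-driven dose changes and the pregnancy-test footnotes require withholding; the maintenance-phase weighing interval is also stated inconsistently

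*Protocol*

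**What the plan says.** Section 5.5.5 of the protocol is a single sentence: "Investigational or other treatment dose adjustments and/or interruptions are not permitted". It has no exception and no cross-reference.

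Two other places give sites mandatory instructions:

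- **Weight groups.** Section 3.1 (Treatment Period) states that after two consecutive visits in a new group "the subject will receive dosing according to the new (higher or lower) weight group respectively", and that "The dose will be adapted starting from the visit of the second consecutive weight change". Section 1.1 of both SAP versions repeats the rule.
- **Pregnancy test.** Table 6-1, footnote 8: "If there is a positive urine pregnancy test, study treatment must be withheld and a serum pregnancy test done at the same visit". Table 6-2, footnote 5, gives the same instruction for Years 2-4.

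Other places presuppose changes or interruptions without requiring them:

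- Section 7.1 lists "secukinumab treatment interrupted/withdrawn" among possible responses to an adverse event.
- Section 8.3 has dosage changes tracked in the IRT.
- Protocol 9.5.2 plans a summary of adverse events leading to dose adjustment, and SAP 2.8.1 plans one of "adverse events leading to dose adjustment or interruption".

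On weighing, Section 3.1 applies the weight rule in the maintenance phase "from Week 12 onwards as assessed at 4 weekly visits", and then states that "during Weeks 16-52 site visits will be scheduled every 8 weeks". SAP 2.9 describes assessment at Week 12, at Week 16, and bimonthly until Week 52.

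**The concern.** Section 5.5.5 is where a site would look to learn what it may change. Taken literally, it makes a deviation of two things the protocol orders elsewhere. Sites could classify the same act differently, and the safety instruction on withholding is contradicted by the section that governs interruptions.

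The dose changes are not small. Section 3.6 says weight-category dosing is there to keep exposure comparable across weight groups, so the timing of a change matters to the protocol's own rationale. A reader of Section 3.1 would expect the weight group to be checked every 4 weeks after Week 12, which the visit schedule does not provide.

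**Working it through.** **1. The ban against the instructions**

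| Source | Content | Force |
|---|---|---|
| 5.5.5 | No adjustment, no interruption | Absolute |
| 3.1; SAP 1.1 | Dose of the new weight group after two consecutive visits | Mandatory |
| Table 6-1 fn 8; Table 6-2 fn 5 | Withhold after a positive urine test | Mandatory |
| 7.1 | Interruption as a response to an adverse event | Optional |
| 8.3; 9.5.2; SAP 2.8.1 | Tracking and summaries | Presupposes, does not instruct |

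Rows two and three cannot be carried out without breaching row one. Rows four and five are out of line with row one but oblige a site to nothing.

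**2. Size of a weight-driven change (Table 5-1, upward crossings)**

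- Low dose at 25 kg: 75 to 75 mg, no change.
- Low dose at 50 kg: 75 to 150 mg, two-fold.
- High dose at 25 kg: 75 to 150 mg, two-fold.
- High dose at 50 kg: 150 to 300 mg, two-fold.

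The dose doubles in 3 of 4 arm-by-boundary cases.

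**3. Weighing interval in the maintenance phase**

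Site visits from Week 16 in Table 6-1 are Weeks 16, 24, 32, 40, 48 and 52. The gaps are 8, 8, 8, 8 and 4 weeks. This reproduces the stated 8-weekly pattern, apart from the last gap.

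Dosing is 4-weekly: from Week 20 to Week 52 there are (52 − 20)/4 + 1 = 9 doses. Four are on the home list (Weeks 20, 28, 36, 44) and five fall at site visits. Dosing every 4 weeks therefore does not imply weighing every 4 weeks.

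**4. Time from crossing a weight limit to confirmation**

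Suppose a subject crosses within a gap of length g1 and the next gap is g2. The first visit in the new group comes 0 to g1 weeks after the crossing, and the second comes g2 weeks later. The lag is g2 to g1 + g2.

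- 4-weekly weighing: 4 to 4 + 4 = **4-8 weeks**.
- Crossing in Weeks 16-24, 24-32 or 32-40: 8 to 8 + 8 = **8-16 weeks**.
- Crossing in Weeks 40-48 (confirmed at Week 52): 4 to 8 + 4 = **4-12 weeks**.
- Crossing in Weeks 48-52 (confirmed at Week 64): 12 to 4 + 12 = **12-16 weeks**, within the general 8-16 range.

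**The case against.** **The ban may be aimed only at discretionary changes.** Weight-band dosing defines each arm. Weight is entered into the IRT at each visit, and the IRT allocates medication and tracks dosage changes. This makes it unlikely that a weight change would be blocked in practice, and that much stands. But 5.5.5 does not limit itself in this way, and an interruption for an adverse event, listed in 7.1, is itself discretionary.

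**Withholding might be read as discontinuation.** Section 5.6.2 requires discontinuation for pregnancy. The footnotes describe an earlier step, taken on the urine result while a serum test is done. If that test is negative and dosing resumes, an interruption has occurred.

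**Section 7.1 and the SAP tables impose nothing on sites.** This is correct. Counting adjustments or interruptions does not authorise them, so these places support the point but do not carry it.

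**The weight rule works as it stands,** because it fires on two consecutive visits with a weight measurement, whichever visits those are. This largely stands, and it is why the 4-weekly phrase is secondary.

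Two stronger inferences are tempting and not supported:

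- *That sites would keep dosing through an event.* Section 5.6.2 requires discontinuation where the investigator judges that an adverse event prevents continuing, and Section 11.1 expects immediate safety action even if it departs from the protocol.
- *That the long intervals in Years 2-4 are part of the contradiction.* For the extension, Section 3.1 refers to scheduled site visits, which agrees with Table 6-2. Nor does the lag there reach 32 weeks, as doubling a 16-week gap would suggest. From Week 52 the gaps run 12, 12, 12, 16, 12, 12, 12, 16, 12, 12, 12, 16, and no two 16-week gaps are adjacent. The longest lag is 12 + 16 = 28 weeks, and it is the stated design.

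**Conclusion.** The contradiction is real and present in the current text: an unconditional ban in 5.5.5 against two mandatory instructions, in Section 3.1 and in the pregnancy-test footnotes. The weighing inconsistency is a lesser, separate point. In the maintenance phase, confirmation generally takes 8-16 weeks (4-12 for a crossing between Weeks 40 and 48), where the 4-weekly wording implies 4-8.

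A reader might infer that the primary result is at risk. For weight-driven changes it is not. They apply only from Week 12, and Sections 5.5.4 and 6.4 place that visit's assessments before its dose, so the co-primary and key secondary endpoints are unaffected. The consequences are for site conduct and safety instructions, classification of deviations, exposure, and PK and long-term summaries by dose and weight group. Even there the SAP covers part of the ground: Section 2.9, and the footnote to Table 2-1 in the 2023 version, say how a subject is counted after a dose change.

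The lag figures assume that visits fall on schedule, that the subject stays in the new weight group at both visits, and that the maintenance phase ends at Week 52, as SAP 2.9 suggests (the protocol does not define maintenance or extension among its three periods). The documents do not say how often weight changes or interruptions are expected, so the number of subjects affected cannot be given.

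**What to change.** The sponsor should reconcile Section 5.5.5 with Section 3.1, Table 6-1 footnote 8, Table 6-2 footnote 5 and Section 7.1, so that one rule states which dose changes and interruptions are allowed. The adverse-event summaries in protocol 9.5.2 and SAP 2.8.1 should then use the same terms.

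Separately, the maintenance-phase weighing frequency in Section 3.1 should be reconciled with Table 6-1 and SAP 2.9. The extension wording needs no change.

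The cost is clarifying wording, with no new procedures. Which dose or clinical rule is right is for the sponsor, and no view is taken here.
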